
In order to standardize the appetitive/metabolic conditions of the study participants, we also plan the following:

- Nutrition Department staff at the NIH Clinical Center will meet with the participants to perform a 24-hour recall of everything the participant consumed prior to admission. Participants will also be instructed to eat as similarly as possible during the 24 hours prior to each of their visits #2-5; capturing the 24-hr recall will allow for checking compliance with this. (This is not meant to say that all participants have to eat the same foods, just that participant '001' should eat the same things each time and participant '002' should eat the same things each time, even though '001' and '002' will be eating different things.). Information on food intake and related calorie intake during the entire stay in our Unit at the Clinical Center will be also recorded.
- Participants will be given a choice of a few lunch and breakfast options, but all options will be the same in kcal and macronutrient content. Tentatively, each participant will receive the same meals for all the visits (e.g., if participant '001' picks lunch A for the first visit, s/he will get lunch A for all her/his visits.), although participants' requests to change their choice among the given options may be satisfied.

Blood Sampling:

Furthermore, at admission at each visit (Visit #2-5), we will also collect blood samples in order to control appetitive/metabolic indicators prior to the initiation of the dietary regimen.

Specifically, during the PR sessions and the fMRI/alcohol clamp sessions, at baseline we will collect:

*Blood Test Panel I: blood glucose, cholesterol, triglycerides, GH, insulin, IGF-1, cortisol, ACTH, PRL, FSH, LH, testosterone total and free, T3-free, T4-free, TSH;

**Blood Test Panel II: GH, insulin, cortisol, PRL and other feeding-related (or stress-related hormones). During ghrelin/placebo/ETOH infusions, Blood Test Panel II will be repeated every 30 minutes during the PR sessions and every 15 minutes during the fMRI/alcohol clamp sessions. In addition, BAC will be measured twice while participants are in the scanner.

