The timepoints for blood collection in the flowsheets of this protocol represent the maximum number of blood sampling for this protocol. While our ideal goal is to collect all of them, we appreciate that occasionally blood collection may be missed due to expected technical problems during the study procedures. Furthermore, if there are blood draw issues with both IV lines, we might also attempt to draw blood using regular or butterfly needles.

Samples will be stored for subsequent analyses of ghrelin levels and other appetitive hormones (and stress hormones), including (but not limited to) insulin, leptin and GLP-1. Some of these stored samples will be shipped in a fully de-identified form to AI [name]'s laboratory to be processed for a metabolic panel that includes appetitive and stress peptides like ghrelin, insulin, leptin, GLP-1 and others. No samples will be shipped until MTA is fully executed between NIAAA and URI. Furthermore, additional metabolic indicators (e.g. glucose, cholesterol, triglycerides, thyroid hormones) will also be assessed prior to the initiation of the dietary regimen.

Overnight stays (visits #2-5)

This study will enroll non-treatment seeking heavy drinking outpatient individuals. Nonetheless, two overnight stays will take place in the Clinical Center (e.g. Metabolic Unit or NIAAA-LCTS inpatient unit, pending on availability) per each session:

- The night before each session, i.e. Visits #2-5. This allows for controlling for two important factors in this study:
 - i) Alcohol consumption before each session, which includes the IV administration of alcohol and ghrelin. In fact, while the baseline BrAC allows for controlling a recent consumption of alcohol, the overnight staying allows for a much longer and thus more rigorous control of alcohol consumption, thus standardizing alcohol consumption across all participants. Additionally, the overnight stay before Visits #2-5 increases the feasibility of the study as it does assure that baseline BrAC will be 0.00 before each session. In fact, if participants came to the clinic on the same day of the session, there is a risk that their BrAC could be positive, which, in turn, would require delaying the session or indeed withdraw the subject if BrAC was > 0.08 ;

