While all steps are always taken to ensure quality data from all participants, we may ask participants who generate unusable data (or if there is an equipment failure) on one of their experimental sessions to repeat that session. This will have the effect of maximizing the risk/benefit ratio as it will prevent having to discard usable data from one session and will minimize the number of participants recruited overall to obtain sufficient data to meet power requirements. We may ask the participant to return at a later date or to stay an additional night on the clinic unit. Subjects will receive additional compensation if experimental sessions are repeated; compensation for this *as needed* research procedures may vary based on the inconvenience units and will be based on the NIDA/NIAAA recommendations.

5. Storage of data and samples

Data will be stored on an NIH data server, under the management of the ORIT, NIAAA. The existence and types of information contained in the data management system have been publicly reported as required by the FOIA.

It should be mentioned that the timepoints for the data collection outlined in the flowsheets of this protocol represent the maximum number that will be collected. While our ideal goal is to collect all of them, we appreciate that occasionally questionnaires and other data collection may be missed (missing data) as in any clinical study, due to time constraints resulting from possible technical problems during the study procedures (e.g., a problem with the IV line or with the computer used to administer questionnaires, etc.).

Plasma and serum for blood levels of ghrelin, GH and other feeding-related and stress-related hormones will be collected from each subject on repeated occasions, as detailed in the study flow sheets. Blood not processed via the Department of Laboratory Medicine at the Clinical Center or will be in -80 freezers. All biological specimens obtained under this protocol will be stored in coded form (protocol plus subject number) in freezers located in the access-controlled laboratory area of LCTS.

Additional blood samples will be collected for DNA extraction and future genetic analysis under the NIAAA Screening Protocol (PI: [name]. Genetic analyses include loci encoding pro-ghrelin (GHRL) and its receptor (GHSR).

6. Additional Considerations

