NCI Common Terminology Criteria for Adverse Events v. 3.0 will be used for grading and reporting adverse events.¹⁶⁷

Criteria for individual subject withdrawal

- A Serious Adverse Event (SAE) that is judged by the Investigators as being related to the study drug;
- Pregnancy;
- At the discretion of the Principal Investigator (PI) based on adverse event (AE) severity;
- Non-compliance with protocol procedures or investigator request(s);
- Patient request.

Enrolled subjects who show up with positive UDT or BrAC $\geq 0.08\%$ at one of the four experimental sessions (excluding the night before visits 2-5) will not perform the session. In this case, the experimental session may be re-scheduled at the PI discretion. Additionally, a session may be rescheduled for other medical reasons for which the PI and/or MAI think it is in the best interest of the participant to re-schedule the session. However, if the subject will repeatedly show up with positive UDT or BrAC $\geq 0.08\%$ at repeated visits, the PI may withdraw him/her from the study.

9. Outcome measures

a. Primary outcome measures

The primary measure of this study will be the breakpoint, which is the schedule (number of button presses) at which the individual stops to work for more alcohol during the PR sessions.

b. Secondary outcome measures

Alcohol exposure will be measured via BrAC exposure measures, i.e. highest BrAC, average BrAC and the area under the BrAC-time curve and by BAC when subjects are in the fMRI scanner. Alcohol craving will be measured using the Alcohol Visual Analogue Scale (A-VAS) and the Alcohol Urge Questionnaire (AUQ). Sensitivity to alcohol will be measured using the Drug Effects Questionnaire (DEQ), Biphasic Alcohol Effects Scale (BAES), and the Profile of Mood States (POMS), repeatedly during the PR session and the CASE Experience Questionnaire (CEQ)

at the end of all sessions. fMRI BOLD signal in brain areas associated with incentive salience and areas associated with reward circuitry (including the ventral striatum) will be measured during the “fMRI/alcohol clamp” session.

10. Statistical Analysis

1. Analysis of data/ study outcomes

Analysis of data/study outcomes

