Outcome data will be examined for homogeneity of variance, and if necessary transformed to meet this criterion. Most of the analyses will consist of repeated measures ANCOVAs to accommodate dependent measures assessed at multiple time points. When the dependent measure is just assessed once then a regular ANCOVA will be used. We will examine medication main effects across several different dependent measures.

Criteria for significance

A probability level of 0.05 or lower will be considered significant.

2. Power analysis

Power analysis

A generic calculation of power for a two-means comparison to detect an effect size of Cohen's $f \geq 0.4$ (large effect size) with a sample size of 50 yields a power estimate ≥ 0.80 at alpha=0.05. The relative effect size chosen (“large” effect size) for the power calculation is based on the observation that laboratory studies typically yield larger effect sizes than clinical trials, including, for example, our recent (unpublished; PI: [name]) human lab studies using the

IV Alcohol PR procedure, described above and representing the study our primary aim (number of button presses) is based upon.

Furthermore, the sample proposed here provides sufficient power (power estimate ≥ 0.80 at alpha=0.05) to detect ghrelin's effects on fMRI BOLD activation in the VS, consistent with the unpublished data (PI: [name]; data already mentioned above) with varenicline (n = 8) vs. placebo (n = 7) indicating significantly higher BOLD activation in the varenicline group.

Accrual number request, taking into account screening/ dropouts

In the Brown University study with IV ghrelin, inclusionary/exclusionary criteria were similar and about 50% of the subjects screened were eligible and randomized. Consistent with other human laboratory studies with a similar study length, we also expect that a number up to 20% will not complete the study. Therefore, we anticipate a number-needed-to-screen of 124 subjects, with 62 being randomized and 50 completers.

11. Human Subjects Protection

a. Subject selection

Adults who fulfill the qualification criteria will be included, regardless of race, ethnicity, sex, or religious affiliation.

b. Justification for inclusion of children

Children will not be included because the study proposed involves the administration of alcohol. It is illegal to give alcohol to individuals below 21 years of age.

c. Justification for inclusion or exclusion of other vulnerable subjects

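### Missed time points are expected, but the method named for the repeated scales excludes incomplete participants in its classical form, and no alternative is given

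*Combined protocol and SAP*

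**What the plan says.** Section 10 (Statistical Analysis, item 1) sets the method: "Most of the analyses will consist of repeated measures ANCOVAs to accommodate dependent measures assessed at multiple time points". An ordinary ANCOVA is used when an outcome is assessed once. The section names no covariates, covariance structure, estimation method or rule for incomplete records.

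Two other places expect incomplete records:

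- Section 5 (Storage of data and samples) says that "occasionally questionnaires and other data collection may be missed (missing data) as in any clinical study", and gives the cause: "due to time constraints resulting from possible technical problems during the study procedures".
- Section 4d (Blood Sampling) says that "occasionally blood collection may be missed due to expected technical problems during the study procedures".

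On frequency, Section 4d says that "Blood Test Panel II will be repeated every 30 minutes during the PR sessions and every 15 minutes during the fMRI/alcohol clamp sessions". Section 9b lists A-VAS and AUQ for craving, and DEQ, BAES and POMS for sensitivity to alcohol, the latter group repeated during the PR session. The text gives no number of scale time points. The flow sheets that would show it are not in the reviewed text.

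Section 10 allows for up to 20% non-completion (62 randomised, 50 completers). Section 4f allows a session with unusable data to be repeated. No passage describes imputation, a mixed model, an analysis set or a sensitivity analysis.

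**The concern.** The plan foresees gaps within sessions and then names a method that, in its classical form, needs a complete set of values from each person. In this crossover that means every time point in both PR sessions. One missed AUQ would then remove all of that participant's AUQ data, including the points that were collected.

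Three things are at stake for the secondary scales, and for any hormone analysis done the same way:

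- **Precision.** The chance that a participant is complete falls with each added time point, and the sample size has no allowance for gaps within completers.
- **Comparability.** Each scale would be analysed in its own subset, so craving and alcohol-response results might not describe the same people.
- **Bias.** If misses were related to response, the complete participants would no longer represent everyone studied.

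**Working it through.** **1. The plan's own power figure.** Inputs from Section 10: Cohen's f = 0.4, N = 50, alpha 0.05 (taken as two-sided), two-means comparison. For two means d = 2f = 0.8, with 25 per group. The noncentrality is 0.8 × √(25/2) = 2.83. Power is 0.807 by the normal approximation and 0.791 by the noncentral t, so the stated 0.80 reproduces. The accrual also reproduces: 62 × 0.8 = 49.6, about 50 completers.

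**2. A paired benchmark.** The design is within-subject, so the loss is shown on a paired t test. I assume dz = 0.40, which gives power 0.792 at n = 50, close to the plan's figure. This dz is my assumption, not the plan's.

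**3. Participants left if any miss excludes.** With miss rate m per point and K points over both PR sessions, and misses independent, the expected number complete is n = 50 × (1 − m)^K. Both m and K are assumed: 5 to 8 scale points per session, so K = 10 to 16.

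| m | K = 10: n | power at dz 0.40 | K = 16: n | power at dz 0.40 |
|---|---|---|---|---|
| 1% | 50 × 0.904 = 45 | 0.75 | 50 × 0.851 = 43 | 0.73 |
| 3% | 50 × 0.737 = 37 | 0.66 | 50 × 0.614 = 31 | 0.58 |
| 5% | 50 × 0.599 = 30 | 0.56 | 50 × 0.440 = 22 | 0.43 |

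The effect detectable with 80% power rises from dz 0.40 at n = 50 to 0.44, 0.52 and 0.63 at n = 43, 31 and 22.

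For hormones, draws every 30 minutes over 120 minutes give 4 or 5 per session, so 8 to 10 over both PR sessions. At K = 8 and 5%, 50 × 0.663 = 33 remain, with power about 0.61.

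**4. If misses cluster.** A failed line or computer would probably remove neighbouring points together. If 5% of points are lost in blocks of four (four blocks over 16 points), 50 × 0.95^4 = 41 remain. If whole sessions are lost, 50 × 0.95^2 = 45 remain. Power at dz 0.40 is then about 0.71 and 0.75.

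**5. If the paired effect is larger.** Reading the plan's d = 0.8 as a difference between two session means, dz = 0.8/√(2(1 − ρ)), where ρ is the within-person correlation. That is 0.57 at ρ = 0 and 0.80 at ρ = 0.5. Power at n = 31 is then 0.86 or 0.99, and at n = 22 it is 0.72 or 0.95.

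**6. Bias and recovery.** A simulation used 3,000 runs, 50 participants, two sessions of five points, a true difference of 0.40 and assumed variances. The session mean of the available points stood in for a mixed model.

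- With 5% of points missing purely at random, power was 0.73 on full data, 0.52 on complete cases and 0.73 using all available points.
- With random misses at 2%, 5% and 10%, complete-case estimates averaged 0.39 to 0.41, so there was no bias.
- When a high previous score made the next point more likely to be missed, complete-case estimates fell to 0.35 to 0.37. All available points gave 0.39 to 0.41.

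**The case against.** The strongest reply is that the plan never says it will drop anyone. It names a family of methods without a procedure, and some analysts use the term repeated measures ANCOVA for a mixed model. A reader might infer that Section 10 prescribes listwise deletion. It does not: exclusion is how the classical method behaves, and the plan is silent. That silence is the point that stands, because gaps are foreseen and nothing says how they are handled.

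A reader might also infer that the results will be biased because intoxicated or sedated participants miss questionnaires. The documents do not support that. Sections 4d and 5 attribute misses to technical problems. Section 7 and the criteria for suspending procedures do allow sessions or infusions to be stopped for adverse events or significant symptoms, and Section 11d expects ghrelin to raise self-infusion. A link to treatment is therefore conceivable, but no passage connects stopped sessions with missed questionnaires.

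The lower power figures can be challenged too. Miss rates, number of points, independence and dz are all assumed, and clustering or a larger dz shrinks the loss considerably. That objection stands, and it is why a range is given.

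Finally, lost participants are already budgeted for through 62 randomised, and sessions may be repeated (Section 4f) or rescheduled (Section 8). That answers the loss of whole sessions. It does not recover a single missed point within an otherwise usable session.

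**Conclusion.** The concern holds as an avoidable loss of precision in the secondary craving and alcohol-response scales (A-VAS, AUQ, DEQ, BAES, POMS), conditional on the named method being applied in its classical form. Hormones come in only if analysed the same way; Section 9b does not list them as outcomes.

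The size cannot be fixed from the documents. It runs from slight (43 to 45 of 50 left at 1% missed) to serious (22 to 30 left at 5%) under independent misses and 10 to 16 points. If misses cluster as in step 4, about 41 to 45 remain at 5%. The power figures apply at dz 0.40 only.

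Bias is possible only if misses relate to response or to stopped sessions; it is not shown. It would also be wrong to read this as a threat to the primary result: the breakpoint is one value per session, and missed scale or blood points do not touch it.

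**What to change.** For outcomes with several time points per session, replace repeated measures ANCOVA in Section 10 with a likelihood-based linear mixed model that uses every observed point:

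- **Fixed effects:** treatment, time, treatment-by-time, session order and the pre-infusion baseline value where one is collected. The plan should say what happens if that baseline is itself missed, since a missing covariate would again remove data.
- **Random effects:** participant, and session within participant.
- **Missing data:** state that the model assumes missing at random, and add a sensitivity analysis covering misses related to response or to a stopped session.

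For once-per-session outcomes such as the breakpoint, any mixed model should carry treatment, session order and a random participant effect only. With one value per session, a session-within-participant effect cannot be separated from residual error.

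If a mixed model was intended all along, saying so and specifying it in these terms is enough. No new data or procedures are needed. The cost is some extra analysis work, and reliance on missing at random and on the chosen covariance structure.

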- 9) Unable to provide a negative urine drug screen.
- 10) Pregnancy or intention to become pregnant for women. Female participants will undergo a urine beta-hCG test to ensure they are not pregnant.
- 11) Use of prescription or OTC medications known to interact with alcohol within 2 weeks of the study. These include, but may not be limited to: isosorbide, nitroglycerine, benzodiazepines, warfarin, anti-depressants such as amitriptyline, clomipramine and nefazodone, anti-diabetes medications such as glyburide, metformin and tolbutamide, H2-antagonists for heartburn such as cimetidine and ranitidine, muscle relaxants, anti-epileptics including phenytoin and phenobarbital codeine, and narcotics including darvocet, percocet and hydrocodone. Drugs known to inhibit or induce enzymes that metabolize alcohol should not be used for 4 weeks prior to the study. These include chlorzoxazone, isoniazid, metronidazole and disulfiram. Cough-and-cold preparations, which contain anti-histamines, pain medicines and anti-inflammatories such as aspirin, ibuprofen, acetaminophen, celecoxib and naproxen, should be withheld for at least 72 hours prior to each study session.
- 12) Current or prior history of alcohol-induced flushing reactions.
- 13) Contraindications for MRI scanning, including metal in body that are contraindicated for MRI (such as implants, pacemaker, prostheses, shrapnel, irremovable piercings), left-handedness, and claustrophobia.

Please also see eligibility checklist (Attachment).

Clearance for eligibility to this protocol will be consistent with the recent “*NIAAA/LCTS Patient Eligibility Checklist Process*” policy implemented by the NIAAA Clinical Director. As such, eligibility criteria will be reviewed by a team of three individuals: research nurse coordinator (or designee), a nurse practitioner and PI or AI designated by the PI. All three signatures will be required in order to establish participants’ eligibility to this protocol.

4. Study Design and Methods:

a. Study overview

The study is designed as a within-subject, double-blind, placebo-controlled randomized clinical trial of ghrelin with non-treatment seeking heavy drinking volunteers. Including screening and follow-up evaluations, the study lasts about 8 weeks and will require five visits to the NIH CRC. The five visits will be as follow and performed in a counter-balanced order across participants:

- Visit #1 - Initial screening visit (**under the NIAAA 98-AA-0009 or 14-AA-0181 protocol**);

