- Visit #2 - Alcohol PR + ghrelin/placebo;
- Visit #3 - Alcohol PR + placebo/ghrelin;
- Visit #4 - fMRI/alcohol clamp + ghrelin/placebo;
- Visit #5 - fMRI/alcohol clamp + placebo/ghrelin;

Visit #6 - Post-study follow-up.

b. Recruitment

Participants will be recruited through referrals from the NIH Volunteer Office, and from the Patient Recruitment and Public Liaison (PRPL) Office as well as through ResearchMatch.org (facilitated through PRPL). ResearchMatch is a voluntary service that matches people interested in being research participants with researchers conducting a wide range of studies.

ResearchMatch is currently used for other protocols of our Clinical Program at NIAAA, as well as for many other NIH protocols. ResearchMatch is a Clinical and Translational Science Awards (CTSA) initiative funded by the National Center for Advancing Translational Sciences, part of the National Institutes of Health.

Furthermore, participants will also be recruited by word of mouth and through local advertisements. Advertisement language will be used as flyers with tear off tabs, posted on the NIH campus, campuses of universities and colleges in the greater Washington DC area, as well as in billboards of public places and public transportation services in the greater Washington DC area. Advertisements will also be posted in electronic and printed local media, including newsletters, websites and local newspapers in the greater Washington DC area (for example, the 'Express'). Listserv ad will be used on craigslist.org, under the volunteers' section, as well as in NIH and other local email distribution lists, that are moderated, and following approval from the managers of these lists. 'ClinicalTrials.gov' may also represent a source of recruitment.

Finally, participants will also be recruited via the NIAAA Screening Protocol (98-AA-0009, PI: [name].), or 14-AA-0181 as the 98-AA-0009 and 14-AA-0181 protocols serve as the screening platform not only for this study but also for any other NIAAA protocol..

c. Screening

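### Section 10 names no session-order (period) term for breakpoint, although ghrelin/placebo order is randomized over the two PR sessions

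*Combined protocol and SAP*

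**What the plan says.** Section 4a (Study overview) describes a within-subject trial with visits "performed in a counter-balanced order across participants". The first PR session (Visit 2) is on ghrelin or placebo, and the second is listed as "Visit #3 - Alcohol PR + placebo/ghrelin". Section 4c randomizes participants to one of two counterbalanced orders, stratified by gender. Section 9 makes breakpoint the primary outcome; each PR session yields one value.

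The analysis text in Section 10 is one short paragraph:
- On assumptions: "Outcome data will be examined for homogeneity of variance, and if necessary transformed to meet this criterion".
- On the model: "Most of the analyses will consist of repeated measures ANCOVAs to accommodate dependent measures assessed at multiple time points", and "When the dependent measure is just assessed once then a regular ANCOVA will be used".
- On the effect of interest: "We will examine medication main effects across several different dependent measures".

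It lists no covariate and no factor other than medication. No period, session, order or sequence term appears there or elsewhere in the supplied text. The other influences on self-administration that the protocol mentions (genotype, chosen activity, sweet preference) are exploratory.

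**The concern.** Counterbalancing makes a change between sessions cancel from the mean ghrelin-placebo difference when the two orders finish equal in size. It does not take that change out of the residual. If participants press more, or less, the second time they meet the task, one order's differences move up and the other's move down. An analysis without period counts that spread as noise. The interval is then wider than it need be and the test conservative. If the orders finish unequal in size, part of the change also enters the drug contrast.

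The trial already randomizes order, so the information needed to remove this is collected in any case. What is at stake is precision on the primary outcome, plus a modelling choice that is better fixed before the data are seen.

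**Working it through.** **Inputs from the documents.** Section 10 gives alpha 0.05 (taken as two-sided), f = 0.4, 50 completers, and accrual "with 62 being randomized and 50 completers". The Introduction (PR IV Alcohol Procedure) reports high between-session correlations in an earlier PR study but no coefficient and no change in mean; its Figure 3 is not in the supplied text.

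**Assumptions.** The shift p (second session minus first) is 0.25, 0.5 or 0.75 in units of the SD of the within-subject difference. Differences are normal.

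**The plan's own figure.** It is introduced as "A generic calculation of power for a two-means comparison to detect an effect size of" f of at least 0.4, with power of at least 0.80. For two means, d = 2f = 0.8. With 25 against 25, the noncentrality is 0.8 × √(25/2) = 2.83, and power is 0.791 (t, 48 df) or 0.807 (normal approximation). Fifty pairs at a paired dz of 0.4 have the same noncentrality, 0.4 × √50 = 2.83, and power 0.792. The stated power reproduces and is not in dispute.

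**Model.** The ghrelin-minus-placebo difference is tau + p in one order and tau − p in the other, with SD 1. Without period: a one-sample t on 50 differences (49 df). With period: the average of the two order means, with pooled SD (48 df).

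**Interval width at 25/25.** The apparent variance is 1 + p² × 50/49, so the width ratio is its square root:
- p = 0.25: √1.064 = 1.03
- p = 0.5: √1.255 = 1.12
- p = 0.75: √1.574 = 1.25

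**Type I error at 25/25 without period.** 0.044, about 0.03 and about 0.015, against 0.05 with period.

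**Power at 25/25.** If d = 0.8, then dz = 0.8/√(2(1 − rho)), which is 0.566 at rho = 0 and 0.8 at rho = 0.5.

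| True effect | No period: p = 0.25 | p = 0.5 | p = 0.75 | With period |
|---|---|---|---|---|
| dz = 0.566 (d = 0.8, rho 0) | 0.97 | 0.96 | 0.93 | 0.975 |
| dz = 0.8 (d = 0.8, rho 0.5) | >0.999 | >0.999 | 0.999 | >0.999 |
| dz = 0.404 | 0.78 | 0.73 | 0.63 | 0.80 |

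The value 0.404 is not in the documents. It is the paired effect that gives 80% power with 50 pairs.

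**Unequal orders.** The bias in the contrast is p × (n1 − n2)/n.
- 28/22: the bias is p × 6/50 = 0.12p. At p = 0.5, type I error is 0.043. Power at dz = 0.566 is 0.90 in the adverse direction and 0.98 in the other, against 0.97 with period. At dz = 0.404 it is 0.58 and 0.85, against 0.79.
- 30/20: the bias is p × 10/50 = 0.20p. Type I error is about 0.06, 0.07 and 0.08 at the three shifts.

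**How likely such splits are.** Suppose 12 of 62 drop out at random from 31/31. A split of 28/22 or worse, in either direction, has probability 0.106; 30/20 or worse has about 0.003. Averaged over all splits, type I error without period is about 0.045, 0.03 and 0.02. At p = 0.5, average power is 0.95 (dz = 0.566) or 0.72 (dz = 0.404), close to the 25/25 values, so most of the loss comes from the error term and little from imbalance.

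**Cost if there is no shift.** At dz = 0.404, power goes from 0.7996 without period to 0.7993 with it.

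**The case against.** **The paragraph leaves the model open.** A reader might infer that Section 10 tests medication alone and shuts period out. The text does not say that. It is generic, and a repeated measures ANCOVA could include order. This stands: the claim is only that period is not pre-specified. A reader might also take the rule for measures assessed once to mean an unpaired breakpoint comparison. Breakpoint is measured in both PR sessions of each participant, so the repeated measures rule is the natural one.

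**No shift is documented, and the larger ones are big.** The protocol claims good test-retest reliability, and the figure that might show the means is not available here. High correlation is compatible with any mean shift, so this does not settle the matter, but it does leave the benefit unknown. Section 4d describes a ladder from 2 to about 15,000 presses over 20 exposures, a factor of (15,000/2)^(1/19) = 1.60 per step. If the SD is 4 steps and rho is 0.5 (both assumed), the SD of the difference is 4 × √(2 × 0.5) = 4 steps. Shifts of 0.25, 0.5 and 0.75 SD are then 1, 2 and 3 steps, or 1.6-, 2.6- and 4.1-fold changes in required presses. At one step and dz = 0.404 the loss is two power points.

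**At the planned effect little is lost.** This stands if f = 0.4 means d = 0.8, most clearly at the correlations the Introduction calls high.

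**Drop-out is overstated for breakpoint.** The 20% covers the whole study, while breakpoint needs only Visits 2 and 3. Sections 4f and 8 also allow sessions to be repeated or rescheduled. Imbalance is probably smaller than computed above.

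**Conclusion.** The point holds as a free improvement. Section 10 does not pre-specify period for breakpoint in a trial that randomizes order over two sessions. If there is a shift and period is omitted, the interval is about 3% to 25% wider at 25/25 over the assumed range, and the test is conservative. The power loss is at most about 5 points if d = 0.8 with uncorrelated sessions, and negligible at rho = 0.5. It reaches 2 to 17 points only if the true effect is near a paired dz of 0.40.

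Two stronger readings are tempting, and the documents support neither. One is that the planned test has an inflated error rate. It stays at or below 0.05 at 25/25, at 28/22 and on average over random drop-out; it exceeds 0.05 only after a markedly uneven split such as 30/20, which is rare. The other is that the trial is underpowered. The stated power reproduces, and no change in N follows.

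The absence of a period term in the supplied text is certain. The size of the benefit rests entirely on an assumed shift.

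**What to change.** State in Section 10 that breakpoint, transformed if needed, is analysed as a within-subject crossover, with drug and session order (period) as fixed effects and participant as the blocking or random effect. Add session order to the repeated measures models for the questionnaires given during the PR sessions.

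This takes two sentences and one degree of freedom. No participants, visits or procedures are added.
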